10.5.4 Immunogenicity Analyses

Assessment of the long-term neutralising and anti-spike protein IgG responses, including seroconversion rates, following vaccination with ARCT-021 is the secondary objective of the study. The assays and study endpoints for these analyses include:

Assays:

- Neutralising antibody responses based on hCoV-19/Singapore/2/2020 isolate:
 - Plaque reduction neutralising titers (PRNT) and/or
 - pseudovirus neutralization test and/or
 - surrogate virus neutralization test (sVNT) and/or
 - microneutralization test.
 - Exploratory: testing using other SARS-CoV-2 isolates may also be performed.
- Binding antibody responses: Total IgG against the full-length SARS-CoV-2 recombinant spike protein and/or spike protein subunits will be assessed using an immune-Luminex and/or ELISA assay.

Endpoints:

- Neutralising and binding antibody responses at Day 29 (6 months after last dose of ARCT-021), Day 197 (12 months after last dose of ARCT-021), Day 281 (15 months after last dose of ARCT-021) for Cohort 2:
- Neutralising and binding antibody responses at Day 1, Day 15, Day 29 (1 month after last dose of ARCT-021), Day 57 (2 months after last dose of ARCT-021), Day 169 (6 months after last dose of ARCT-021), Day 365 (12 months after last dose of ARCT-021) for Cohort 1
- T cell responses (Flow cytometry and ELISpot assays) at Day 29 and Day 197 (Cohort 2)
- T cell responses (Flow cytometry and ELISpot assays) at Day 1, Day 15, Day 29, Day 169, Day 365 (Cohort 1: ARCT-021-02 vaccinated participants)

Descriptive statistics, by assessment time point, will be used to describe all immunogenicity results and further specified in the SAP prior to data analysis. Statistical testing, if performed, will be prespecified in the final SAP and will be exploratory in nature.

10.5.5 Clinical Events of Special Interest Analyses

Statistical analyses of CESIs will be descriptive over timepoint in the safety and longitudinal safety populations. These endpoints include confirmed COVID-19 (including severe cases) and asymptomatic SARS-CoV-2 infection over timepoint and also analyzed as pooled and separately for the younger and older adult groups.

10.5.6 Missing Data Handling

Due to the exploratory nature of this study and the lack of statistical testing, missing data will not be imputed. Values that are below the level of quantification will be recoded to zero for analysis purposes.

11 INVESTIGATOR'S REGULATORY OBLIGATIONS

11.1 Informed Consent

The written informed consent document should be prepared in the language(s) of the potential subject population and approved by the Sponsor or designee.

Before a subject's participation in the trial, the Investigator is responsible for obtaining written informed consent from the subject after adequate explanation of the aims, methods, anticipated benefits, and potential hazards of the study and before any protocol-specific screening procedures or any Study Drug are administered. Explanation of the theoretical risks of enhanced COVID-19 disease as a consequence of ARCT-021 administration will be included as part of informed consent process for all subjects who will be receiving ARCT-021 in the study. The subject must be given sufficient time to consider whether to participate in the study.

The acquisition of informed consent and the subject's agreement or refusal to notify his/her primary care physician should be documented in the subject's medical records and the informed consent form should be signed and personally dated by the subject and by the person who conducted the informed consent discussion (not necessarily an Investigator). The original signed informed consent form should be retained in the Study Master File and in any other locations required by institutional policy, and a copy of the signed consent form should be provided to the subject.

11.2 Ethical Conduct of the Study

The study must be conducted in compliance with this clinical study protocol, Good Clinical Practices (GCP), as outlined by ICH E6(R2), as well as the demands of national drug and data protection laws and all applicable local and national regulatory requirements.

11.3 Independent Ethics Committee/Institutional Review Board

A copy of the protocol, proposed informed consent forms, other written subject information, and any proposed advertising material must be submitted to the IEC/IRB for written approval. A copy of the written approval of the protocol and informed consent form must be received by the Sponsor or designee before recruitment of subjects into the study and shipment of Study Drug. A copy of the written approval of any other items/materials that must be approved by the Study Center or IEC/IRB must also be received by the Sponsor or designee before recruitment of

subjects into the study and shipment of Study Drug. The Investigator's Brochure must be submitted to the IEC/IRB for acknowledgement.

The Investigator must submit to and, where necessary, obtain approval from the IEC/IRB, for all subsequent protocol amendments and changes to the informed consent document. The Investigator should notify the IEC/IRB of deviations from the protocol in accordance with ICH GCP, as outlined by ICH E6(R2). The Investigator should also notify the IEC/IRB of SAEs occurring at the Study Center and other AE reports received from the Sponsor or designee, in accordance with local procedures.

The Investigator will be responsible for obtaining annual IEC/IRB approval/renewal throughout the duration of the study. Copies of the Investigator's reports, all IEC/IRB submissions and the IEC/IRB continuance of approval must be sent to the Sponsor or designee.

11.4 Subject Confidentiality

The Investigator must ensure that the subject's confidentiality is maintained. On the case report forms or other documents submitted to the Sponsor or designee, subjects should be identified by initials (if permitted by local law) and a subject identification number only. Documents that are not for submission to the Sponsor or designee (e.g., signed informed consent forms) should be kept in strict confidence by the Investigator.

In compliance with Federal and local regulations/ICH GCP, as outlined by ICH E6(R2) Guidelines, it is required that the Investigator and institution permit authorized representatives of the company, of the regulatory agency(s), and the IEC/IRB direct access to review the subject's original medical records for verification of study-related procedures and data. Direct access includes examining, analyzing, verifying, and reproducing any records and reports that are important to the evaluation of the study. The Investigator is obligated to inform and obtain the consent of the subject to permit named representatives to have access to his/her study-related records without violating the confidentiality of the subject.

12 ADMINISTRATIVE AND LEGAL OBLIGATIONS

12.1 Protocol Amendments

Protocol amendments must be made only with the prior approval of the Sponsor or designee. Agreement from the Investigator must be obtained for all protocol amendments and amendments to the informed consent document. The regulatory authority and IEC/IRB must be informed of all amendments and give approval for any amendments likely to affect the safety of the subjects or the conduct of the trial. The Investigator **must** send a copy of the approval letter from the IEC/IRB to the Sponsor or designee.

12.2 Study Termination

The Sponsor or designee reserves the right to terminate the study. The Investigator reserves the right to terminate their participation in the study, according to the terms of the site contract. The Investigator should notify the IEC/IRB in writing of the trial's completion or early termination and send a copy of the notification to the Sponsor or designee.

12.3 Study Documentation and Storage

An electronic case report form (eCRF) utilizing an Electronic Data Capture (EDC) application will be used for this study.

The Investigator should ensure that all appropriately qualified persons to whom he/she has delegated trial duties are recorded on a Sponsor-approved Delegation of Site Responsibilities Form.

Source documents are original documents, data, and records from which the subject's case report form data are obtained. These include but are not limited to hospital records, clinical and office charts, laboratory and pharmacy records, diaries, imaging, and correspondence. In this study, eCRF pages may not be used as source documents.

The Investigator and Study Center staff are responsible for maintaining a comprehensive and centralized filing system of all study-related (essential) documentation in accordance with ICH GCP, as outlined by ICH E6(R2), suitable for inspection at any time by representatives from the Sponsor or designee and/or applicable regulatory authorities. Elements should include:

- Subject files containing completed case report forms, informed consents, and supporting copies of source documentation
- Study files containing the protocol with all amendments, Investigator's Brochure, copies of pre-study documentation and all correspondence to and from the IEC/IRB and the Sponsor or designee
- If drug supplies are maintained at the Study Center, proof of receipt, Study Drug Product Accountability Record, Return of Study Drug Product for Destruction, final Study Drug product reconciliation, and all drug-related correspondence

In addition, all original source documents supporting entries in the case report forms must be maintained and be readily available.

No study document should be destroyed without prior written agreement between the Sponsor or designee and the Investigator. Should the Investigator wish to assign the study records to another party or move them to another location, he/she must notify the Sponsor or designee.

12.4 Study Monitoring

The Sponsor representative and regulatory authority inspectors are responsible for contacting and visiting the Investigator for the purpose of inspecting the facilities and, upon request, inspecting the various records of the trial (e.g., case report forms and other pertinent data) provided that subject confidentiality is respected. Remote monitoring may be used for some visits, but 100% source data verification will be performed.

The Sponsor monitor or designee is responsible for inspecting the case report forms at regular intervals throughout the study to verify adherence to the protocol; completeness, accuracy, and consistency of the data; and adherence to local regulations on the conduct of clinical research. The monitor should have access to subject medical records and other study-related records needed to verify the entries on the case report forms.

The Investigator agrees to cooperate with the monitor to ensure that any problems detected in the course of these monitoring visits, including delays in completing case report forms, are resolved.

To ensure the quality of clinical data a clinical data management review will be performed on subject data received by the Sponsor or designee. During this review, subject data will be checked for consistency, omissions, and any apparent discrepancies. In addition, the data will be reviewed for adherence to the protocol and ICH GCP, as outlined by ICH E6(R2). To resolve any questions arising from the clinical data management review process, data queries and/or Study Center notifications will be sent to the Study Center for completion and return to Sponsor or designee.

The Principal Investigator will sign and date the indicated places on the case report form in the EDC. These signatures will indicate that the Principal Investigator inspected or reviewed the data on the case report form, the data queries, and the Study Center notifications, and agrees with the content.

12.5 Site Audit

In accordance with ICH GCP, as outlined by ICH E6(R2) and in accordance with the Sponsor's audit plans, this study may be selected for audit by representatives (or designees) from the Sponsor. Inspection of Study Center facilities (e.g., pharmacy, drug storage areas, laboratories) and review of study-related records may occur to evaluate the trial conduct and compliance with the protocol, ICH GCP, as outlined by ICH E6(R2) and applicable regulatory requirements.

12.6 Language

Case report forms must be completed in English. Generic names and trade names are acceptable for concomitant medications. Combination medications should be recorded using their trade name.

All written information and other material to be used by subjects and investigative staff must use vocabulary and language that are clearly understood.

12.7 Compensation for Injury

The Sponsor maintains appropriate insurance coverage for clinical trials and will follow applicable local compensation laws. Subjects will be treated and/or compensated for any study-related illness/injury in accordance with the information provided in the Compensation for Injury section of the Informed Consent document.

14 APPENDICES

APPENDIX 1: SCHEDULE OF ASSESSMENTS

Appendix 1: Schedule of Assessments

1. Screening

Subjects who Received Placebo or a Single Injection of ARCT-021 in Parent Study

Study Week/Day	D -28 to D -1
Visit Window (Days)	0
Informed Consent	X
Inclusion/Exclusion	X
Body Weight	X
Physical Exam ¹	X
Vital Signs ²	X
Pregnancy Test ³	X
Chemistry Panel	X
Hematology	X
Coagulation	X
HbA1c	X
Urinalysis ⁴	X
Immunogenicity ⁵	X
Drug/Alcohol Screen ⁶	X
SAE, CESI, NOCD and MAAE ⁷	X
Concomitant Medications and Procedures ⁸	X
SARS-CoV-2 questioning ⁹	X

1 Full physical exam

2 BP, HR, RR, temp

3 Women who are not surgically sterile or post-menopausal. Dipstick acceptable

4 Dipstick test per local procedures. If abnormal send sample to laboratory for microscopy.

5 This is only PRNT50 for the screening visit

6 Urine test.

7 SAE, CESI, NOCD and MAAE that occurred since completion of the Parent Study and screening for this study will be recorded. For subjects that received ARCT-021 in the Parent Study, these will be entered as SAE/CESI/MAAE in the EDC. For subjects that received placebo in the Parent Study these will be recorded as medical history.

8 Concomitant medications and procedures since completion of the Parent Study and screening for this study will be recorded for all subjects.

9 Subjects will be questioned about symptoms of COVID-19 and exposure to confirmed COVID-19 or confirmed SARS-CoV-2 infection cases amongst household contacts, friends, work contacts and other contacts.

Subjects who Received Two Injections of ARCT-021 in Parent Study

Study Week/Day	D -28 to D -1
Visit Window (Days)	0
Informed Consent	X
Inclusion/Exclusion	X
Body Weight	X
Physical Exam ¹	X
Vital Signs ²	X
SAE, CESI, NOCD and MAAE ³	X
Concomitant Medications and Procedures ⁴	X
SARS-CoV-2 questioning ⁵	X

- 1 Full physical exam (assessment of heart, lungs, abdomen, eyes, ears, nose and throat, head and neck, musculoskeletal, lymphatic, injection site, dermatologic, neurologic, extremities)
- 2 BP, HR, RR, temp
- 3 SAE, CESI, NOCD and MAAE that occurred since completion of the Parent Study and screening for this study will be recorded
- 4 Concomitant medications and procedures since completion of the Parent Study and screening for this study will be recorded
- 5 Subjects will be questioned about symptoms of COVID-19 and exposure to confirmed COVID-19 or confirmed SARS-CoV-2 infection cases amongst household contacts, friends, work contacts and other contacts.

2. Assessments After the Screening Period

Subjects Not Receiving ARCT-021 in This Study

Study Week/Day	Observation Period (40 Weeks)				
	W1 D1	W5 D29	W13 D85	W29 D197	W41 D281/or Early Term*
Visit Window (Days)	0	±7	±7	±14	+14
Physical Exam ¹	X		X	X	X
Vital Signs ²	X		X	X	X
Archived plasma sample ³	X	X	X	X	X
Archived serum sample ³	X	X	X	X	X
Archived PBMC sample ³	X	X	X	X	X
Immunogenicity		X		X	X
T-cell responses		X		X	X
SAE, CESI, NOCD and MAAE ⁴	X	X	X	X	X
SARS-CoV-2 questioning ⁵	X	X	X	X	X
Counselling about long-term follow-up for SARS-CoV-2 infection ⁶					X

***Subjects that terminate early should complete all procedures for Study Day 281**

- 1 Abbreviated physical exam (assessment of vitals, heart, lungs, lymphatic, abdomen and symptom directed examination, if any symptoms) to be given during observation period to assess changes from screening.
- 2 BP, HR, RR, temp
- 3 Stored at -70 °C for follow up immunological assessments or exploration of laboratory findings and/or adverse events
- 4 SAE, CESI, NOCD and MAAEs will be recorded.
- 5 At each visit, subjects will be questioned about symptoms of COVID-19 and exposure to confirmed COVID-19 or confirmed SARS-CoV-2 infection cases amongst household contacts, friends, work contacts and other contacts.
- 6 Subjects that terminate from the study before completion will be told to inform the study site staff if they develop symptoms compatible with COVID-19 (Section 6.2.4) or a diagnosis of SARS-CoV-2 infection or COVID-19 for one year after vaccination so that they can be adequately followed up.

Subjects Receiving a Single Injection of ARCT-021 in This Study

Study Week/Day	Study Drug Administration	Post-Treatment Period (52 Weeks)							
		W1 D1	W2 D8	W3 D15	W5 D29	W9 D57	W25 D169	W37 D253	W53 D365/ Early Term*
Visit Window (Days)	0	±1	±1	0	±7	±14	±14	+14	
Physical Exam ¹	X ^a	X	X	X	X	X	X	X	X
Vital Signs ²	X ^a	X	X	X	X	X	X	X	X
Pregnancy Test ³	X ^a								
Chemistry Panel	X ^a	X	X	X					
Hematology	X ^a	X	X	X					
Coagulation	X								
HbA1c	X								
Urinalysis ⁴	X ^a	X		X					
Archived plasma sample ⁵	X ^a			X	X	X	X	X	X
Archived serum sample ⁵	X ^a			X	X	X	X	X	X
Archived PBMC sample ⁵	X ^a		X	X	X	X	X	X	X
Immunogenicity	X ^a			X	X	X			X
T-cell responses	X ^a		X	X		X			X
Drug/Alcohol Screen ⁶	X ^a								
Study Drug Administration	X								
Review of symptom diary ⁷		X	X						
Unsolicited AE	X	X	X	X					
SAE, CESI, NOCD and MAAE ⁸	X	X	X	X	X	X	X	X	X
Concomitant Medications and Procedures	X	X	X	X					
SARS-CoV-2 questioning ⁹	X	X	X	X	X	X	X	X	
Counselling about long-term follow-up for SARS-CoV-2 infection ¹⁰									X

***Subjects that terminate early should complete all procedures for Study Day 365**

- 1 Full physical exam to be given at Day 1 and Day 365/Early Termination; abbreviated physical exam (assessment of vitals, heart, lungs, lymphatic, abdomen and symptom directed examination, if any symptoms) to be given during treatment and follow-up period to assess changes from screening. Injection site to be inspected at all visits after injection until resolution of local reactogenicity event(s).
- 2 BP, HR, RR, temp
- 3 Women who are not surgically sterile or post-menopausal. Dipstick acceptable
- 4 Dipstick test per local procedures. If abnormal send sample to laboratory for microscopy.
- 5 Stored at -70 °C for follow up immunological assessments or exploration of laboratory findings and/or adverse events
- 6 Can be done at the site using established methods, e.g., a breathalyzer or urine test.

- 7 Symptom diary to be reviewed on Day 8. If subject has any unresolved local or systemic reactogenic events then they should be instructed to continue to complete the symptom diary for a further week and the symptom diary should be reviewed again at Day 15. This review includes specifically asking about injection site and systemic (fever, fatigue, headache, chills, nausea, vomiting, diarrhoea, new or worsened myalgia, and new or worsened arthralgia) events. If not being completed for the second week after injection, then the symptom diary will be collected on Day 8; otherwise symptom diary to be collected on Day 15.
- 8 Only SAE, CESI, NOCD and MAAE will continue to be recorded after Day 29.
- 9 At each visit, subjects will be questioned about symptoms of COVID-19 and exposure to confirmed COVID-19 or confirmed SARS-CoV-2 infection cases amongst household contacts, friends, work contacts and other contacts.
- 10 Subjects that terminate from the study before completion will be told to inform the study site staff if they develop symptoms compatible with COVID-19 (Section 6.2.4), or a diagnosis of SARS-CoV-2 infection or COVID-19 for one year after vaccination so that they can be adequately followed up.

Time (time is in reference to Study Drug administration):

a Pre-dose

If not specifically labeled, "X" means anytime

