Any recorded temperature $\geq 38^{\circ}\text{Celsius}$ ($\geq 100.4^{\circ}\text{ Fahrenheit}$) or injection site erythema/swelling $\geq 25\text{mm}$ in size will be reported as an adverse event and graded according to Toxicity Grading Scale for Healthy Adult and Adolescent Volunteers Enrolled in Preventive Vaccine Clinical Trials, Sept 2007.

Solicited events with onset within 7 days of injection will be considered related.

Symptom diaries will be collected at the Day 8 or 15 (depending on completion status) visits for the first injection and 36 or 43 visits for the second injection and will serve as source documents.

For those subjects who received ARCT-021 in the Parent Study:

At Screening, SAEs, NOCDs, CESIs and MAAEs occurring between completion of the Parent Study and the Screening visit for this study will be solicited and recorded in the EDC to ensure continuity of safety follow-up from the Parent Study to this study. Events that occurred prior to dosing in this study will be recorded as medical history.

For subjects who received ARCT-021 in either the Parent Study or this study:

SAEs, NOCDs, CESIs, and MAAEs will be collected for all enrolled subjects for the duration of the study until the Final Visit (Day 365 or Day 281 if vaccinated or not vaccinated with ARCT-021 in this study) or Early Termination visit (if applicable).

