8.8 Withdrawal of Subjects from the Study Procedures

Subjects must be withdrawn from study procedures for any of the following:

- Withdrawal of consent
- The subject is unwilling or unable to comply with the protocol in the judgement of the Investigator

Other reasons for withdrawal of subjects from study procedures might include:

- At the discretion of the Investigator for medical reasons
- Significant protocol deviation
- The subject is lost to follow-up

All efforts will be made to complete and report the observations as thoroughly as possible up to the date of withdrawal. All information, including the reason for withdrawal from study, must be recorded in the eCRF.

For subjects who fail to show up for the final visit, or for three consecutive visits, study staff are encouraged to make at least three documented attempts to contact the subject by telephone and at least one documented written attempt to contact the subject or legal guardian to encourage the completion of study termination procedures. These efforts to contact the subject should be recorded in the source documentation. The termination date for the subject to be captured on the Study Termination eCRF page is the date of the last successful contact (clinic visit or telephone) with the subject. These subjects will be regarded as lost to follow-up.

Any subject who withdraws consent to participate in the study will be removed from further treatment and study observation immediately upon the date of request. These subjects should be encouraged to complete the early termination study procedures and observations at the time of withdrawal ([Appendix 1](#)).

For subjects withdrawn for reasons other than withdrawal of consent every effort should be made to complete the early termination of study procedures and observations at the time of withdrawal (see [Appendix 1](#)).

The reason for withdrawal from the study will be entered in the EDC. If the reason for withdrawal includes one or more AEs then an AE will be entered as the primary reason for withdrawal.

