10.5.3 Safety Analysis

The primary objective of the study is the evaluation of the safety and tolerability of ARCT-021. The primary endpoints that align with this objective are:

- Solicited AEs for 7 days after vaccination (Cohort 1), summarized by toxicity grade
- Unsolicited AEs for 28 days after vaccination (Cohort 1), summarized by mild/moderate/severe and relationship to ARCT-021
- SAEs through Day 197 (Cohort 2; 12 months after ARCT-021 vaccination in ARCT-021-01 study), summarized by relationship to ARCT-021
- SAEs through Day 365 (Cohort 1; 12 months after ARCT-021 vaccination in ARCT-021-02 study), summarized by relationship to ARCT-021
- MAAEs through Day 197 (Cohort 2; 12 months after ARCT-021 vaccination in ARCT-021-01 study), summarized by relationship to ARCT-021
- MAAEs through Day 365 (Cohort 1; 12 months after ARCT-021 vaccination in ARCT-021-02 study), summarized by relationship to ARCT-021
- NOCDs through Day 197 (Cohort 2; 12 months after ARCT-021 vaccination in ARCT-021-01 study), summarized by relationship to ARCT-021
- NOCDs through Day 365 (Cohort 1; 12 months after ARCT-021 vaccination in ARCT-021-02 study), summarized by relationship to ARCT-021
- Safety laboratory assessments through 28 days after vaccination (Cohort 1), summarized by toxicity grade (where relevant)

- Vital signs assessments through day 365 (Cohort 1; 12 months after ARCT-021 vaccination in ARCT-021-02 study) summarized by toxicity grade

To support the continued characterization of ARCT-021 tolerability and safety when administered as a single dose, the following summaries will be provided:

- Summary of solicited (7 days after vaccination) and unsolicited AEs 28 days after vaccination)
- Summary of MAAEs, NOCDs, SAEs through 12 months after vaccination

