SARS-CoV-2 questioning ⁹	X	X	X	X	X	X	X	X
Counselling about long term follow-up for SARS-CoV-2 infection ¹⁰								X

* Participants that terminate early should complete all procedures for Study Day 365.

- 1 Full Physical Exam to be given at Day1 and Day 365/Early Termination; abbreviated physical exam (assessment of vitals, heart, lungs, lymphatic, abdomen and symptoms directed examination, if any symptom) to be given during treatment and follow-up period to assess changes from screening. Injection site to be inspected at all visits after injection until resolution of local reactogenicity event (s).
- 2 BP, HR RR, temp.
- 3 Women who are not surgically sterile or post-menstrual. Dipstick acceptable.
- 4 Dipstick test per local procedures. If abnormal, send sample to laboratory for microscopy.
- 5 Stored at -70°C for follow-up immunological assessment or exploration of laboratory findings and/or adverse events.
- 6 Can be done at the site using established methods, e.g. a breathalyzer or urine test.

- 7 Symptom diary to be reviewed on Day 8. If participant has any unresolved local or systemic reactogenic events, then they should be instructed to continue to complete the symptom diary for a further week and the symptom diary should be reviewed again at Day 15. This review includes specifically asking about injection site and systemic (fever, fatigue, headache, chills, nausea, vomiting, diarrhoea, new or worsened myalgia, and new or worsened arthralgia) events. If not being completed for the second week after injection, then the symptom diary will be collected on Day 8; otherwise, symptom diary to be collected on Day 15.
- 8 Only SAE, CESI, NOCD and MAAE will continue to be recorded after Day 29..
- 9 At each visit participants will be questioned about symptoms of COVID-19 and exposure to confirmed COVID-19 or confirmed SARS-COV-2 infection cases amongst household contacts, friends, work contacts and other contacts.
- 10 Participants that terminate from the study before completion will be told to inform the study site staff if they develop symptoms compatible with COVID-19 (Section 6.2.4), or a diagnosis of SARS-CoV-2 infection or COVID-19 for one year after vaccination so that they can be adequately followed up.

Time (time is in reference to Study vaccine administration):

a Pre-dose

If not specifically labeled, “X” means anytime

10.2 Appendix B: List of Laboratory Analytes.

List of Laboratory Analytes for Which Data Available at this Interim

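### The early-termination visit for vaccinated subjects schedules no safety labs and no diary retrieval for those who leave before Day 29, and its omission of unsolicited AEs and concomitant medications contradicts the protocol text

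*Protocol*

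**What the plan says.** The schedule for subjects receiving ARCT-021 in this study (Protocol Appendix 1) ends in a single column headed "W53 D365/ Early Term". Its footnote reads "Subjects that terminate early should complete all procedures for Study Day 365". SAP Appendix A has the same table and rule: "Participants that terminate early should complete all procedures for Study Day 365". Neither makes the content of the visit depend on when the subject leaves.

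Protocol Section 8.8 sends withdrawing subjects to that schedule. Unless the subject has revoked consent, it asks that "every effort should be made to complete the early termination of study procedures and observations at the time of withdrawal", with a reference to Appendix 1.

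Protocol Section 10.5.3 lists the primary safety endpoints. Three fall within the first 28 days after dosing:
- reactogenicity, given as "Solicited AEs for 7 days after vaccination (Cohort 1), summarized by toxicity grade"
- other reported events over a longer window, given as "Unsolicited AEs for 28 days after vaccination (Cohort 1), summarized by mild/moderate/severe and relationship to ARCT-021"
- laboratory results, given as "Safety laboratory assessments through 28 days after vaccination (Cohort 1), summarized by toxicity grade (where relevant"

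On the diary, Section 6.2.1 states "Symptom diaries will be collected at the Day 8 or 15 (depending on completion status) visits for the first injection", and makes the diaries source documents. Protocol Section 10.5.6 and SAP Section 5.4 both rule out imputation of missing data.

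**The concern.** The Day 365 column is built for someone a year past vaccination, when routine safety bloods and the reactogenicity diary are long finished. Applied to someone who leaves on Day 5 or Day 12, it calls for antibody, T-cell and archive samples but no safety labs, although blood is being drawn and the primary lab window is still open.

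What is at stake is the completeness of two primary endpoint components in a small group. The protocol shows why labs cannot be replaced by interview. Section 2.3 reports reversible, asymptomatic grade 3 lymphopenia after a single 7.5 µg dose in the parent study, which only a blood count detects. Table 2 gives liver-test monitoring to 28 days as the hepatic mitigation, again citing Appendix 1. SAP Section 8.2 builds its shift tables on lab grades that worsen within 7 days of vaccination.

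**Working it through.** There is no sample size, power or dropout figure to reproduce. The check is a row-by-row reading of the schedule against the text.

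**Step 1. The schedule against the rest of the protocol** (visits after Day 1; the Protocol and SAP tables agree on these rows).

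| Item | Marked at | In Day 365/Early Term column | Does other text fill the gap? |
|---|---|---|---|
| Chemistry, hematology | Days 8, 15, 29 | No | No. Section 6.2 promises samples to 28 days but defers to Appendix 1; Section 8.8 also defers to it; Section 8.5 speaks of monitoring throughout but sets no draw |
| Urinalysis | Days 8, 29 | No | No, for the same reasons |
| Diary review and collection | Days 8, 15 | No | No. Section 6.2.1 and the Appendix 1 diary footnote tie both to Day 8 or Day 15 |
| Unsolicited AEs | Days 8, 15, 29 | No | Yes. Section 6.2.1 collects them at every study visit; Section 9.4.3 records non-serious AEs to 28 days after dosing |
| Concomitant medications and procedures | Days 8, 15, 29 | No | Yes. Sections 8.9.1 and 8.9.2 require them to 28 days after dosing |

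The first three rows are therefore gaps. The last two are contradictions between table and text.

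**Step 2. What is lost, by last scheduled visit completed.**

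| Last visit completed | Post-dose chemistry/hematology draws lost | Post-dose urinalyses lost | Diary |
|---|---|---|---|
| Day 1 (leaves before Day 8) | 3 of 3 | 2 of 2 | Neither reviewed nor collected |
| Day 8 (leaves before Day 15) | 2 of 3 | 1 of 2 | First week already reviewed; an extended diary is not collected |
| Day 15 (leaves before Day 29) | 1 of 3 | 1 of 2 | No loss |

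Nominal Day 8 is 8 − 1 = 7 days after dosing. A subject leaving before that visit therefore has no scheduled post-dose value for the 7-day shift table in SAP Section 8.2.

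**Step 3. Possible size.** The documents give neither the number dosed in this study (N) nor the number leaving before Day 29 (k). Both are assumptions here. The share of dosed subjects with incomplete labs is k/N.

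| Assumed N | k = 1 | k = 3 |
|---|---|---|
| 30 | 1/30 = 3.3% | 3/30 = 10.0% |
| 60 | 1/60 = 1.7% | 3/60 = 5.0% |
| 99 | 1/99 = 1.0% | 3/99 = 3.0% |

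The last row uses the approximate total enrolment in Protocol Section 3.6. Cohort 1 is only part of those enrolled, because two-dose recipients from the parent study are not dosed again.

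**The case against.** The strongest reply is that a reader could take far more from the blank column than the documents support. Most of that reply stands.

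- *That unsolicited AEs and concomitant medications go uncollected in early leavers.* Not supported. Sections 6.2.1, 8.9.1, 8.9.2 and 9.4.3 require them, and an early-termination visit is a study visit.
- *That diary data are lost for anyone leaving in the first 28 days.* Not supported. Whoever attended Day 8 has had the 7-day solicited data reviewed.
- *That primary safety data are lost in the most informative withdrawals.* Not supported. If AEs are among the reasons for withdrawal, Section 8.8 makes an AE the primary recorded reason, and SAP Section 8.1.7 requires listings and narratives. The visit still captures SAEs, MAAEs, NOCDs and CESIs, with a full physical exam and vital signs. The injection site is inspected until local events resolve. Subjects must report grade 3 or worse solicited AEs at once (Section 3.8).
- *That lost events are counted as non-events throughout.* Not supported. SAP Section 8.1.9.1 states a whole-cohort denominator for unsolicited TEAE tables, the family whose collection the text already requires. SAP Sections 8.1.9.2 and 8.2 state none for solicited events or labs.

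It can also be said that plasma and serum are archived at the visit and that Section 3.8 allows extra visits. Archived plasma and serum cannot give a blood count or urinalysis, and extra visits are for AEs or abnormal results already known. Neither closes the gap for a leaver with no reported event.

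Finally, the remedy reaches only those who attend. Section 8.8 merely encourages subjects who withdraw consent to complete the visit, and those lost to follow-up attend nothing. That limits the benefit but does not justify the omission.

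**Conclusion.** The point holds for safety labs and diary retrieval. A site following the stated rule would take no final chemistry, hematology or urinalysis from a dosed subject leaving before Day 29. It would have no scheduled point to retrieve the diary from one leaving before Day 8, or before Day 15 if the diary was extended. Both feed primary Cohort 1 endpoints, and nothing is imputed. For unsolicited AEs and concomitant medications or procedures, the defect is a table that contradicts the text.

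The effect is probably small. Under the assumed counts, 1.0% to 10.0% of dosed subjects would have an incomplete lab record. That range shows scale only and rests wholly on the assumptions. It is not an estimate of bias in any reported incidence, and the documents give no count of, or reasons for, early withdrawals. The change is worth making because it is cheap and specific, not because the primary safety analysis is in serious doubt.

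**What to change.** Change the early-termination footnote in Protocol Appendix 1 and SAP Appendix A. A subject dosed in this study who terminates before completing the Day 29 visit should have:

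- the Day 365/Early Termination procedures;
- the Day 29 chemistry, hematology and urinalysis;
- review and collection of any symptom diary not yet collected.

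Mark unsolicited AEs and concomitant medications and procedures at that visit too, so that the table matches Sections 6.2.1, 8.9.1, 8.9.2 and 9.4.3.

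The cost is one footnote in each document and one already planned set of bloods and urine, at a visit where blood is drawn anyway, for the few who leave early and agree to attend. It recovers nothing from those who are lost or decline.

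SAP Section 4.4 already expects Day 57 data for Cohort 1. If all of Cohort 1 has passed Day 29, report instead how many dosed subjects left before completing that visit, and which post-dose labs and diaries they had.
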